6.3.3. Electrolyte Abnormalities

Electrolyte abnormalities are common adverse events with Silmitasertib (CX-4945) which may predispose subjects to arrythmias.

- a. Mandatory 5-HT3 antagonist pre-medication may compound this effect. To adequately monitor for this risk, a 24-hour telemetry monitoring for subjects with electrolyte abnormalities may be performed, if clinically indicated.
- b. Use of atropine as an anti-diarrheal medication may also compound this effect. Investigator should consider use of another anti-diarrheal agent for subjects who have persistent diarrhea despite use of loperamide.

6.4. SILMITASERTIB (CX-4945) DRUG INTERACTION

6.4.1. Effect of CX-4945 in Human Liver Microsomes

The absorption, distribution, metabolism, and excretion (ADME) properties of CX-4945 have been evaluated in in vivo to support nonclinical safety evaluations and to assess the potential relevance to humans. CX-4945 was tested in a non-GLP in vitro ADME-TOX in human liver microsomes with the following seven key CYP450 isoenzymes: CYP1A2, CYP2B6, CYP2C8, CYP2C9, CYP2C19, CYP2D6 and CYP3A4. CX-4945 did not show significant inhibition or induction of any CYP isoenzymes tested in this study (for all isozymes more than 80 percent remained after 60 minutes and it was not possible to calculate a specific half-life).

The result suggests that CX 4945 does not inhibit or induce these seven CYP450 isozymes, and can therefore be safely co-administered with drugs that are metabolized via this pathway.

Antiemetic drugs (5-HT3 antagonist) are required and anti-diarrheal drugs are recommended for concomitant use in the treatment group A for management of possible GI toxicities. CYP3A4 is the predominant enzyme pathway for ondandestron and granisteron metabolism. Loperamide is metabolized by the cytochrome P450 (CYP) system and is a substrate for the CYP3A4 isoenzyme. Approximately 200 subjects have been treated with CX-4945 in Phase I/II clinical trials to date and approximately 115 subjects received required and /or recommended concomitant treatment with

CONFIDENTIAL Page 34 of 66

antiemetic and antidiarrheal drugs. CX-4945 was safely co-administered with concomitant medications with no drug-drug interaction (DDI) observed.

Because complete CX-4945 metabolism information is not available at this point and treatment with 5-HT3 antagonist and anti-diarrheal drugs is planned for treatment arm A, current use or anticipated need for drugs that are known strong inhibitors or inducers of major CYP enzymes should be avoided from Day 1 through Day 14. If the replacement is not possible, then patients taking strong inhibitors or inducers of major CYP enzymes should not be enrolled to the study (exclusion criterion #6).

CONFIDENTIAL Page 35 of 66

7. STUDY DISCONTINUATION

7.1. SUBJECT COMPLETION

A participant is considered to have completed the study if he or she has completed the treatment phase and follow-up visits at Day 28, Day 45, and Day 60. Documentation to whether or not each subject completed the clinical study will be recorded.

7.2. SUBJECT WITHDRAWAL FROM PARTICIPATION

At any point during the study and without prejudice to future care, all subjects have the right to withdraw from participation, refusing to complete scheduled study assessments and follow-ups. The reason for withdrawal from participation will be recorded in the subject medical records.

All patients who discontinued therapy but maintain consent for study participation to be followed for outcome information and should remain in the study through the end of assessment and follow-up period for all important safety and anti-viral activity data collection and evaluation. The only reasons for withdrawal from participation should be withdrawal of consent and loss to follow-up. Before a subject is identified as lost-to-follow up, the site should make all reasonable efforts to contact the subject. These attempts must be documented and should include at a minimum one phone call and one certified letter.

7.3. SUBJECT DISCONTINUATION FROM STUDY TREATMENT

The Investigator can discontinue a subject from study therapy at any time if in his clinical judgment considers to be medically necessary. Investigators considering discontinuing study treatment should contact the medical monitor prior to such discontinuation. The reason(s) for discontinuation of study treatment should be documented in sourse records. Subjects who have study treatment discontinued will continue to be followed, per protocol, whenever possible. If visits to the site are not possible after discharge, subjects can be followed via telehealth or other approaches (telephone calls, e-mails, and texts) to ascertain vital status in all subjects.

Subjects who have study treatment discontinued due to a serious adverse event will be followed until resolution or stabilization of the event.

Discontinuation from the study therapy does not mean the withdrawal from participation. Every attempt should be made to collect follow-up information to minimize missing data in this study.

An investigator may discontinue a participant from the study therapy for the following reasons:

- Pregnancy
- Significant study therapy non-compliance
- If any clinical adverse event (AE) or serious adverse event (SAE), laboratory abnormality, or other medical condition or situation occurs such that continued treatment under the protocol would not be in the best interest of the participant

CONFIDENTIAL Page 36 of 66

- Disease progression which requires discontinuation of the study therapy
- Significant study therapy non-compliance
- Withdrawal of consent from study treatment

In the event that a subject is withdrawn from the study treatment at any time due to an adverse event or SAE, the procedures stated in Section 8.3 (Safety) must be followed.

CONFIDENTIAL Page 37 of 66

8. STUDY ASSESSMENTS AND PROCEDURES

The study will have three phases: Screening Phase/Visit, Treatment Phase, and Follow-Up Phase. A schedule of assessments and procedures is provided in **Section 1.3**.

Due to risk of infection for study staff and hospital personnel, the site may take steps to limit face-to-face interaction (i.e. telehealth or eSignature).

8.1. STUDY PROCEDURES

8.1.1. Screening Period:

The subject will sign and date the informed consent form (ICF) and Health Insurance Portability Accountability Act (HIPAA) authorization (according to site policy and practices) prior to any study-related procedures. The study center will maintain the study-specific screening and enrollment logs at their site.

For screening procedures see the Schedule of Activities in Section 1.3 and Assessments in Section 8.2.

8.1.2. Treatment Period:

For the treatment period procedures see the Schedule of Activities in Section 1.3 and Assessments in Section 8.2.

Subjects who meet the eligibility criteria will be randomized prior to any other Day 1 study procedures. The following evaluations and assessments should be performed on Day 1prior to treatment: review of any changes in medication history, physical examination, vital signs, clinical status – ordinal scale assessment, EQ-D5-5L questionnaire, pulse oxygen saturation (SpO2), PT-PCR, laboratory sample collection for routine serum biochemical, hematologic, coagulation, and IL6 levels analysis.

Patient follow-up should continue after discharge via approaches available to the site staff (e.g., telehealth visits, COVID-19 outpatient clinic, telephone calls, texts, and emails to the patient and close contacts). These efforts should prevent missing data while limiting additional public health risks and unnecessary community exposure.

During the treatment phase, subjects randomized to the treatment arm A will receive CX-4945 (1000 mg) twice a day for up to 14 days. Details on study drug administration can be found in **Section 6**.

8.1.3. Follow Up Period

CONFIDENTIAL Page 38 of 66

For follow-up procedures see the Schedule of Activities in **Section 1.3** and Assessments in **Section 8.2**.

8.1.4. Unscheduled Visits

In the event that the subject will return to clinic at a time other than a regularly scheduled study visit, the visit will be regarded as an unscheduled visit. Assessments at unscheduled visits are at the discretion of the Investigator. All pertinent findings, including adverse events or changes in medications, will be noted in the subject medical records.

8.2. ASSESSMENTS

Every effort should be made to ensure that the protocol-required tests and procedures are completed as described. However, it is anticipated that from time to time there may be circumstances outside of the control of the Investigator that may make it unfeasible to perform the test. In these cases the investigator will take all steps necessary to ensure the safety and well-being of the patient. When a protocol-required test cannot be performed, the investigator will document the reason for this and any corrective and preventive actions that he or she has taken to ensure that normal processes are adhered to as soon as possible. The study team will be informed of these incidents in a timely manner.

8.2.1. Safety Assessment

Safety assessments will include collection of AEs, serious adverse events (SAEs), vital signs and physical examination, electrocardiogram (ECG [12-lead]), laboratory assessments, including pregnancy tests and verification of concomitant treatments.

8.2.1.1. Pregnancy Testing

All pregnancy tests used in this study, either urine or serum, must have a sensitivity of at least 25 mIU/mL and must be performed by a certified laboratory. For female patients of childbearing potential, a negative pregnancy test is required before receiving CX-4945 (1 negative pregnancy test at screening). Following a negative pregnancy test result at screening, appropriate contraception must be commenced: the study candidate should have used 2 forms of contraception. Pregnancy tests will also be repeated at Day 14 to confirm that the patient has not become pregnant during the study. Pregnancy tests will also be done whenever 1 menstrual cycle is missed during the study and when potential pregnancy is otherwise suspected. In the case of a positive confirmed pregnancy, the patient will be withdrawn from administration of investigational product but may remain in the study.

8.2.1.2. Adverse Events

CONFIDENTIAL Page 39 of 66

Assessment of adverse events will include the type, incidence, severity (graded by the CTCAE version 5.0) timing, seriousness, and relatedness. For AE assessment details, see **Section 8.3.3**. Investigator will follow-up for any AEs/SAEs and mortality status at Day 28, Day 45 and Day 60.

8.2.1.3. Vital Signs and Physical Examination

Patients will have a full physical examination to include an examination of all major body systems, height (at screening only), weight, blood pressure and pulse rate, which may be performed by a physician, registered nurse or other qualified health care provider, as acceptable according to local regulation. A symptom-directed physical examination should be limited to systems of primary relevance (i.e., cardiovascular, respiratory, and systems associated with symptoms). Changes from baseline abnormalities should be recorded at each subsequent physical examination. New or worsened abnormalities should be recorded as an adverse event.

Pulse oximetry should be collected prior to collection of the blood pressure, pulse rate, and temperature. Oxygen levels should be evaluated on the finger in accordance with the site standard procedures. All abnormalities will be evaluated by the study physician.

Blood pressure, heart rate, respiration rate, and temperature should be recorded after approximately 5 minutes rest. An abbreviated physical exam is an assessment for emergent toxicities or changes from prior visits and a symptom directed exam conducted by a physician, trained physician's assistant or nurse practitioner, as acceptable according to local regulation.

8.2.1.4. Laboratory Safety Assessment

Hematology and blood chemistry will be drawn at the time points described in the Schedule of Activities (see **Section 1.3**) and analyzed at local laboratories. Unscheduled clinical labs may be obtained at any time during the study to assess any perceived safety concerns. Samples for hematology, blood chemistry, coagulation, pregnancy and urinalysis will be analyzed by the site's local laboratory.

Table 4. Safety Laboratory Tests

Hematology	Chemistry	Coagulation	Urinalysis	Pregnancy Test
Hemoglobin	ALT	PT or INR	color, appearance, specific gravity, pH, protein, glucose, occult blood, ketones, leukocyte esterase, nitrite, bilirubin, urobilinogen	For female patients of childbearing potential, serum or urine
Hematocrit	AST			
RBC	Alk Phos			
Platelets	LDH			
WBC	Total Protein			
Absolute Neutrophils	Sodium			

CONFIDENTIAL Page 40 of 66

Hematology	Chemistry	Coagulation	Urinalysis	Pregnancy Test
Absolute Lymphocytes	Potassium		microscopic examination of urine sediment	
Absolute Monocytes	Ferritin			
Absolute Eosinophils	Chloride			
Absolute Basophils	Calcium			
	Bicarbonate			
	Total bilirubin			
	d-dimer			
	Creatine (serum)			
	BUN			
	Albumin			
	C-reactive Protein (CRP)			
	Creatinine Clearance			
	IL-6			
	Creatine Phosphokinase (CPK)			
	eGFR			

8.2.1.5. Electrocardiogram

Electrocardiogram (ECG): ECG will be done at Screening and at Day 14. It is preferable that the machine used has a capacity to calculate the standard intervals automatically, including QT and QTc interval. At each time point (see the Schedule of Activities), if the significant abnormalities (>Grade 2) in ECG intervals are revealed, then the ECGs should be re-evaluated by a qualified person at the site for confirmation as soon as the finding is made, including verification that the machine reading is accurate.

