4.3. END OF STUDY DEFINITION

CONFIDENTIAL Page 25 of 66

A participant is considered to have completed the study if he or she has completed the treatment phase and follow-up visits at Day 28, Day 45, and Day 60.

Discontinuation from the study drug does not mean the withdrawal from the study assessments. Subjects who discontinued therapy should remain in the study and continue follow-up for key outcomes. The only reasons for study withdrawal are withdrawal of consent and loss to follow-up.

CONFIDENTIAL Page 26 of 66

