6.1.3. Dosing and Administration of CX-4945

Patients enrolled to the treatment Arm A will receive 1000 mg of CX-4945 twice daily by mouth, beginning on Day 1, and continuously through Day 14.

Patients will be instructed to take oral antiemetic prophylaxis at least 1 hour prior to taking the study drug. Other oral medications should be taken at least one hour before or 2 hours after ingesting the dose of CX-4945 capsules.

CONFIDENTIAL Page 30 of 66

^{*}SOC and Supportive Care are defined in Section 4.1.

Patients will take five 200-mg CX-4945 capsules twice daily, two hours after the morning meal and two hours after the evening meal (dinner) with water. Patients are advised to take 1 capsule at a time with a pause in between each. This method may prevent a clumping effected in the stomach, so patient can take as much as 10 minutes to swallow each capsule.

The study drug will be taken on an empty stomach with at least six ounces (180 mL) of water. After CX-4945 administration, the patient will be NPO (except for water) for 2 hours, after which, the patient may eat.

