6.1.5. Silmitasertib (CX-4945) Dose Modifications

The most common drug related adverse events reported for CX-4945 are predominantly gastrointestinal disorders, including nausea, vomiting and diarrhea. The dose interruption, reduction, and permanent discontinuation for any toxicity are described below. Dose modification instructions provided bellow do not substitute for investigators' medical judgement. Investigators should always manage their patients according to their medical judgement based on the particular clinical circumstances.

Table 3. Silmitasertib (CX-4945) Dose Modification and Management for potential toxicities (attributable to Silmitasertib)

CTCAE 5.0 Grade (attributable to Silmitasertib)	Treatment Modifications
Grade 1	Treat on time. dose reduction is not required
Grade 2	Hold until≤ Grade 1, resume at same dose
Grade 3	Hold until< Grade 2, resume at dose reduced by 1 level (200 mg)
Grade 4	Hold until Grade 2, resume at dose reduced by 1 level (200 mg).
	Permanent discontinuation can be considered by at the
	Investigator's discretion

• **Dose Reduction:** If a dose-response relationship for toxicity is observed, a reduced dose can be given to the subject. Dose adjustments will be allowed based on the toxicity, efficacy evaluation, and clinical judgment by physician.

CONFIDENTIAL Page 31 of 66

- **Dose Interruption:** Refer to Table 3 above. Recovery to acceptable levels must occur to allow Silmitasertib (CX-4945) continuation.
- **Dose Discontinuation:** Treatment with CX-4945 can be discontinued prematurely due to the following reasons:
 - Disease Progression
 - o Respiratory failure requiring invasive mechanical ventilation,
 - Shock (defined by SBP < 90 mm Hg, or Diastolic BP < 60 mm Hg), or
 - Multiple organ dysfunction/failure
 - Intolerable toxicity most probably attributable to CX-4945.
 - Pregnancy
 - o Significant study therapy non-compliance
 - o If any clinical adverse event (AE), laboratory abnormality, or other medical condition or situation occurs such that continued treatment under the protocol would not be in the best interest of the participant
 - Withdrawal of consent from study treatment or participation

Discontinuation from the study drug does not mean the withdrawal from the study assessments. Subjects who discontinued therapy should remain in the study and continue follow-up for key outcomes. The only reasons for study withdrawal are withdrawal of consent from study participation and loss to follow-up.

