9.2. DESCRIPTION OF STUDY OUTCOMES (ENDPOINTS)

For description of study outcomes see the Objectives and endpoints in Section 3

9.2.1. Safety Measures:

- Incidence and severity of adverse events (AEs)
- Incidence of serious adverse events (SAEs)
- Incidence of AEs and SAEs leading to discontinuation of study medication.
- Changes in blood chemistry (including electrolyte abnormalities), hematology and coagulation parameter results
- Changes in vital signs including temperature, pulse, respiratory rate, systolic and diastolic blood pressure
- Changes in physical examination results
- Changes in electrocardiogram (ECG) results

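### The only scheduled post-baseline ECG is at Day 14, so patients off CX-4945 by then have no scheduled on-drug tracing, yet their off-drug tracing is pooled into the Arm A summary

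*Combined protocol and SAP*

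**What the plan says.** **Schedule.** Section 8.2.1.5 says "ECG will be done at Screening and at Day 14". Table 1 in Section 1.3 marks the 12-lead ECG at the same two visits. Screening falls on Day -7 to Day -1, and Day 14 has a window of one day either side. No ECG is linked to stopping the drug, and there is no early-termination visit.

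**Exposure.** Under Section 6.1.3, Arm A takes CX-4945 "beginning on Day 1, and continuously through Day 14". Section 6.1.5 foresees shorter exposure: "Treatment with CX-4945 can be discontinued prematurely due to the following reasons", followed by a list that includes progression, intolerable toxicity, adverse events and laboratory abnormalities. Table 3 also provides for interruptions, for example at Grade 2: "Hold until≤ Grade 1, resume at same dose".

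**Retention.** Section 6.1.5 says "Discontinuation from the study drug does not mean the withdrawal from the study assessments", and Section 4.3 says "Subjects who discontinued therapy should remain in the study and continue follow-up for key outcomes". The Safety population (Section 9.7.1.3) includes anyone who received at least one dose of CX-4945 or standard of care after randomization.

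**Role and analysis.** ECG results are named in the primary endpoint (Section 3). Section 9.2.1 lists "Changes in electrocardiogram (ECG) results" among the safety measures. Section 9.8.4.3 lists all ECG values and summarises them by arm and visit, without reference to whether the patient was on drug.

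**Reason to look.** Section 6.3.3 calls electrolyte abnormalities common with CX-4945 and a possible predisposition to arrhythmia. Of the 5-HT3 antagonist required in Arm A it adds: "Mandatory 5-HT3 antagonist pre-medication may compound this effect".

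**The concern.** The ECG is timed by calendar day, while any drug effect depends on exposure. A patient who stops on Day 5 and is followed as planned has the only post-baseline ECG about nine days later (14 − 5 = 9). That tracing enters the Arm A summary alongside tracings taken during dosing.

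Two separate things follow. First, the number of on-drug tracings is smaller than the Arm A denominator, so the data support a weaker statement about ECG findings on drug than the table suggests. Second, if an effect fades after stopping, pooling pulls the Arm A result toward no change.

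Gastrointestinal toxicity or electrolyte disturbance could lead both to stopping and to an ECG change. The lost on-drug tracings may therefore not be a random subset. Chemistry is scheduled on Days 1, 4, 8, 11 and 14, so a mid-course electrolyte abnormality can be documented with no scheduled ECG beside it.

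What is at stake is how a clean table is read. Without the split, it could be taken as evidence about the studied dose from all of Arm A when part of it was recorded off drug.

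**Working it through.** There is no figure in the plan to reproduce. Section 9.3 bases the sample size on clinical judgment, and Section 9.8.4 plans no inferential statistics. The calculations below only illustrate size.

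**Inputs**
- Arm A size: 40 randomized 1:1 (Section 9.3), so n = 40/2 = 20.
- d = share of Arm A without an on-drug Day 14 tracing. The documents give no rate, so 0% to 50% is **assumed**.
- True on-drug frequency of an ECG abnormality: 5% and 10%, both **assumed**.

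**Formulas**
- On-drug tracings: m = 20 × (1 − d).
- Chance of seeing at least one abnormality at true frequency p: 1 − (1 − p)^m.
- Exact one-sided 95% upper limit after zero abnormalities: 1 − 0.05^(1/m).

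| d (assumed) | m | At least one seen, p = 10% | At least one seen, p = 5% | Upper limit after zero |
|---|---|---|---|---|
| 0% | 20 | 0.878 | 0.642 | 13.9% |
| 10% | 18 | 0.850 | 0.603 | 15.3% |
| 20% | 16 | 0.815 | 0.560 | 17.1% |
| 30% | 14 | 0.771 | 0.512 | 19.3% |
| 40% | 12 | 0.718 | 0.460 | 22.1% |
| 50% | 10 | 0.651 | 0.401 | 25.9% |

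For example, at d = 20%: m = 20 × 0.8 = 16 and 1 − 0.05^(1/16) = 17.1%.

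**Dilution of a mean change.** Suppose a fraction d of the Arm A tracings is off drug and the effect has fully worn off in them. The pooled mean change is then (1 − d) of the on-drug change, or 0.80 of it at d = 20%. This also assumes that Day 14 ECGs are equally complete in patients on and off drug.

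**Selection, hypothetical.** Suppose the true frequency is 10%, half of the affected patients stop because of the effect, 20% of all patients stop for unrelated reasons, and the effect resolves off drug.
- Still on drug: 0.9 × 0.8 + 0.1 × 0.5 × 0.8 = 0.72 + 0.04 = 0.76.
- Frequency among on-drug tracings: 0.04/0.76 = 5.3%.
- Frequency in the pooled Arm A table: 4.0%.

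In this scenario the split removes the dilution but not the selection, so the on-drug subset must be reported as what it is.

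**Does anything else fill the gap?** Telemetry (Sections 6.3.3 and 8.2.1.6) is optional and meant for patients with electrolyte abnormalities. Assessments at unscheduled visits (Section 8.1.4) are discretionary. Follow-up after discharge may be remote (Section 1.3, footnote 16), so a patient discharged early may have no Day 14 ECG at all. The data monitoring committee's review (Section 9.9) names adverse event listings, deviations and enrolment, but not ECG data.

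**The case against.** A reader might infer that patients who stop early have no on-drug ECG at all, or that the ECG comparison cannot detect a drug effect. The documents support neither. Patients are hospitalised at enrolment, telemetry and unscheduled assessments are allowed, and clinically significant findings made outside the schedule can still be reported as adverse events. What is missing is a *scheduled* on-drug measurement. Patients still dosing at Day 14 do give on-drug data: at 20% off drug, the chance of seeing a 10% abnormality falls only from 0.878 to 0.815. Most of the imprecision comes from having 20 patients.

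A reader might also infer that the ECG table describes mainly patients who tolerated the full course. It does not, because early stoppers remain in it. A patient whose dose was held and resumed, or reduced, can also be on drug at Day 14.

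That early stoppers are the patients most likely to have had an ECG effect is plausible but not established. The listed reasons for stopping include progression, non-compliance, pregnancy and withdrawal of consent. Table 3 provides for resuming after a hold, and Section 2.4 describes the drug as generally well tolerated. The Day 15 edge of the window is minor: the text available to me gives no elimination half-life, so how far off drug such a tracing would be is unknown.

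The most important objection concerns the remedy. Moving the post-baseline ECG to the moment of stopping in Arm A would let toxicity or deterioration set its timing in one arm only. Disease severity could then look like a drug effect. This stands, and it is why Day 14 should remain the between-arm time point.

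Finally, missed doses and reasons for stopping are already documented, and detailed methods are left to a separate SAP. Day-level drug status could probably be derived. But nothing in the documents commits the analysis to using it.

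**Conclusion.** The point holds as a measurement and reporting gap of modest size. The plan provides no scheduled on-drug ECG for Arm A patients who are off CX-4945 at Day 14, and it pools their tracings with on-drug ones in a component of the primary endpoint. Sensitivity is reduced and an on-drug change can be diluted. The documents do not support calling the ECG comparison uninformative.

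Assuming 0% to 50% off drug, 20 to 10 on-drug tracings remain, and the upper limit after zero abnormalities runs from 13.9% to 25.9%, with 17.1% at 20%. These figures rest on the assumed share and on a complete Day 14 ECG for everyone still on drug. The dilution factor also assumes that the effect has fully worn off by the time of the off-drug tracing.

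**What to change.** 1. Keep the Day 14 ECG in both arms as the between-arm comparison. For Arm A, take it before the last CX-4945 dose where feasible.
2. Record the date and time of the last CX-4945 dose with each ECG.
3. In Section 9.8.4.3 and the SAP, add a summary of Arm A ECGs split by on-drug and off-drug status at the tracing, with days since last dose. Base any statement about ECG safety on drug on the on-drug subset, give its n, and label it descriptive because the subset is defined after randomization.
4. If the sponsor-investigator also collects an ECG at early permanent stop, or at discharge when no in-person Day 14 visit is possible, report it separately. Do not substitute it for Day 14 in the between-arm table.

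The cost of items 1 to 3 is one form field, one extra table and a smaller stated n for on-drug ECGs. They add no ECG per patient. If the schedule is left as it is, item 3 can still be adopted in the SAP, which Section 9.8 says will be approved before database lock.
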